4.4 Withdrawal Criteria and Planned Analyses of Withdrawals and Dropouts

The subject will be withdrawn from the study if:

- Prior to the first plasma exchange session, no plasma sample has been collected for possible future assays.
- Any serious adverse event is recorded, advising removal of the subject.
- The subject or his/her legal representative wishes to abandon the study and continue follow-up and normal treatment in the center.
- The investigator is of the opinion that treatment continuation is contraindicated.
- The subject fails to adhere to the study protocol.

The reason for withdrawal of the subject will be documented, and a final visit will be scheduled to obtain blood samples and to complete the pertinent tests. Whenever possible, these tests will be made on the same day as the final visit. No subject can be re-enrolled into the study after having been withdrawn from the study.

4.5 Treatment of Pre-Randomization Losses, Entry Reclassification

Subjects withdrawn in the screening phase will not be able to participate in the trial. As discussed above, no subject will be re-enrolled into the study after having been withdrawn from the study.

4.6 Estimated Duration of the Recruitment Period

The planned trial recruitment period will last approximately 12 months.

5. TREATMENT OF SUBJECTS

5.1 Treatment Regimen

5.1.1 Study Treatment Procedure

After the screening visits, the subject will receive the following treatment:

- One month and a half (6 weeks) of intensive treatment with one full plasma exchange per week (all the three groups)
- Two of the three groups will follow 12 months of maintenance treatment with one low-volume plasma exchange every month combined with IVIG every 4 months administered at the end of the corresponding plasmapheresis instead of albumin (that is, 9 plasmaphereses with Albumin replacement and 3 plasmaphereses with IVIG replacement). During this year patients will follow one of the two different pre-allocated treatment arms: 1) with the doses of albumin and IVIG needed to replace those removed during the plasmapheresis, 2) with half of the doses of albumin and IVIG. (See **Appendix 8**).
- One of the three groups will follow the same schedule as the above two groups but with half of the doses of albumin alone (without IVIG), that is, 12 plasmaphereses with half-dose albumin alone.

Albutein[®] 5% (an approved medicinal product) will be used during the intensive period (full plasma exchanges).

Albutein[®] 20% (an approved medicinal product) will be used during the maintenance period (low-volume plasma exchanges), together with Flebogamma[®] DIF (an approved medicinal product).

5.1.2 Dosage and Treatment Regimen

The six full replacement sessions of the intensive treatment period will be completed in six weeks (one session per week)

The volume of each full plasma exchange will be approximately that of one plasma volume of the patient as calculated from body weight, height and hematocrit (approximately 35-45 mL/kg, corresponding to a volume of 2500-3000 mL).

The 12 low-volume plasma exchange sessions (9 with albumin 20% and 3 with IVIG) of the maintenance treatment period will be completed in 12 months (one session per month).

The volume of each plasmapheresis during the low-volume plasma exchange period will be between 690 and 880 mL of plasma (depending on the patient body weight, following the nomogram for plasma donation used in the USA. (See **Appendix 3**).

5.1.3 Method of Application

Full plasma exchanges (Intensive treatment period)

Full plasma exchanges (FPE) can be carried out via peripheral access or centrally, according to the individual characteristics of the subject. In the latter case, and before the first replacement session, a double-lumen catheter must be placed in the subclavian or jugular vein. Implantation and maintenance will be carried out according to the standard procedures used in each center but it will be mandatory to perform a chest X-ray to confirm the correct placement of the catheter. Removed plasma volume will be replaced with the same volume of Albutein[®] 5% during the procedure.

The removed and replaced plasma volume will depend on patient's characteristics (sex, height, weight and hematocrit). It will be approximately 35-45 mL/kg, corresponding to a volume of 2500-3000 mL. This volume is calculated automatically by the device or manually by the operator depending on the device used.

For blinding the control group, adhesive gauze dressing will be placed on the subclavicular or jugular region, stitching a catheter of characteristics similar to the catheters used in the treatment group (see Appendix 9).

The central catheter has the advantage of increased convenience for the subject during the process, since it allows greater flows and thus shorter session times and obviates the need in each session to perform two peripheral venipunctures. The central line access also facilitates subject mobility during the procedure.

Each session is carried out at a rate of 60-100 mL/min., provided replacement is possible through a double-lumen catheter placed in the subclavian vein, with a continuous-flow cell separator. Each of these sessions will last approximately two to three hours. The control group will be subjected to simulated (sham) plasma exchanges during the same time as the subjects in the treatment group.

Each subject must remain in the facility throughout the procedure and then for as long as necessary to ensure a safe return home.

These details refer to the plasma exchange procedure performed through centrifugation (the most commonly used) although the procedure through filtration is also permitted.

Albutein[®] 5% will be used according to the instructions of the **Full Prescribing Information (Appendix 1)**. The solution is normally clear to slightly opalescent. Do not use the product if the solution is cloudy or has precipitated. The product must be at body temperature before use. Do not dilute with water for injections. Once the container is open, the contents must be administered immediately. Unused contents must be discarded. No remaining product in an opened container can be stored in the refrigerator and used at a later time.

The vital signs of each subject (blood pressure, heart rate, respiratory rate, and body temperature) are to be monitored 15-30 minutes before replacement, during and again 15-30 minutes after the procedure, and as often as considered opportune by the investigator. The coagulation parameters must also be controlled, particularly fibrinogen concentration. In the case of any relevant alteration in the coagulation parameters, replacement must be suspended and no further sessions will be carried out until the parameters return to adequate levels (see sections 5.2.1 and 5.2.2).

Low-volume plasma exchanges (Maintenance treatment period)

In all sites where the low-volume replacement session will be performed, a device based on regular plasma donation (Auto-C, Fenwal, Illinois, USA with FDA PMA approval # BP850001 or Aurora, Fenwal, Illinois, USA with FDA 510(k) clearance # BK110072) will be tested (see **Appendix 3** for device protocol). The Auto-C (FDA PMA approval # BP850001) or Aurora (FDA 510(k) clearance # BK110072) based devices are used with the objective of offering the patient a procedure that is similar to a conventional plasma donation with the difference that albumin or IVIG will be infused at the end of the plasmapheresis.

Low volume plasma exchange (LVPE) will be carried out through a peripheral line. The removed plasma volume will be similar to that of a plasma donation (690 to 880 mL) and will depend on patient's weight.

The control group will undergo simulated (sham) low volume plasma exchange which will last approximately the same time as the subjects in the treatment group.

Albumin

Albutein[®] 20% will be infused at the end of the corresponding plasmapheresis using Auto-C (FDA PMA approval # BP850001) or Aurora (FDA 510(k) clearance # BK110072) based devices. During the Maintenance period the dosing will be as follows:

- 1st arm: 200 mL (40 g, 9 plasmaphereses)
- 2nd arm: 100 mL (20 g, 9 plasmaphereses)
- 3rd arm: 100 mL (20 g, 12 plasmaphereses)

Therefore, after the LVPE (690 to 880 mL of plasma removal), Albutein[®] 20% is infused depending also on patient's weight and treatment arm (200 to 80 mL). Due to the difference in volume (removed/infused), it is advised to infuse saline solution to avoid the risk of hypotension related events (see Appendix 10 for guidance).

The main characteristics of the product can be found in the **Full Prescribing Information (Appendix 1)**. The solution is normally clear to slightly opalescent. Do not use the product if the solution is cloudy or has precipitated. The product must be at body temperature before use. Do not dilute with water for injections. Once the container is open, the contents must be administered immediately. Unused contents must be discarded. No remaining product in an opened container can be stored in the refrigerator and used at a later time.

Intravenous immunoglobulin infusions

Flebogamma[®] DIF will be infused at the end of the corresponding plasmapheresis during the Maintenance period following the instructions of the **Full Prescribing Information (Appendix 2)**. At the discretion of the investigator, patients can be premedicated with paracetamol and antihistamines.

During the Maintenance period the dosing of IVIG will be as follows:

- 1st arm: 20 g
- 2nd arm: 10 g
- 3rd arm: None (only albumin)

5.2 Criteria for Treatment Modification or Interruption

5.2.1 Criteria for Modifying Regimens

In the case of any relevant alteration in the coagulation parameters, full plasma replacement (Intensive period) is to be suspended and no further sessions will be carried out until the parameters return to adequate levels.

Replacement is to be postponed 24 hours if fibrinogen <1 g/L or the prothrombin time (Quick) <60% of the control value.

Platelet depletion to below 100,000/ μ L is also an indication for replacement suspension.

Relevant alterations of coagulation parameters are not expected to occur with the low-volume plasma exchanges (Maintenance period).

If any adverse event occurs during the infusion of Flebogamma[®] DIF one of the following actions will be carried out taking into account the nature and severity of the event:

- To stop the infusion.
- To reduce progressively the infusion rate until the symptoms disappear.

After re-evaluation the adverse event, it can be proceed as follows:

- To restart the infusion or to increase as of a tolerated rate (once the symptoms have disappear) or
- To definitely stop the infusion.

If a patient presents an adverse event two times with the same infusion rate, the following doses will be administered at the maximum tolerated rate.

5.2.2 *Special Warnings and Precautions for Use*

Full plasma exchange is a safe technique that may induce very well-known and therefore preventable and controllable, adverse reactions, according to the guidelines provided below. In any case, and considering the special vulnerability of the patients studied, a number of precautions (in addition to the habitual measures) have been taken to minimize the risks of the procedure:

1. Plasma exchange will be carried out by specialized nursing personnel, under direct and continuous supervision by the specialists.
2. Subjects will be required to remain in the center before and after the procedure for longer periods of time than usual.
3. Vital signs and laboratory test parameters will be monitored more frequently than usual.
4. The treatment suspension / postponement criteria are clearly established.
5. The person accompanying the subject should be present and/or in proximity before, during and after the procedure but not in the same room in order to maintain the blind. Exceptionally, agitated patients could be accompanied by the caregiver during the procedure in the same room to ease patient's anxiety. In this case it is mandatory the subject is scheduled for the treatment a different day than the rest of the patients.

The patient will have direct, 24-hour access to the specialist (by mobile phone) in both the replacement phase and during subsequent follow-up. In the case of any incident, the physician will decide the actions to take.

Adverse effects (AEs) may be observed during the replacement procedure, due to the process of apheresis, the replacement fluid used, or as a result of the patient disease or idiosyncrasy. These AEs include hypocalcemia, hypotension, allergic reaction, coagulation disorders, adverse events related to vascular access, and other AEs such as headache, nausea and anxiety.

The information contained in this and the following sections is also valid for plasma removal (plasmapheresis) during the low-volume plasma exchange period but the expected AE rate is much lower. In fact, the plasmaphereses performed within this period will be very similar to those performed for regular plasma donations (e.g., Grifols performs between 12,000 and 15,000 plasmaphereses for plasma collection daily in the US).

On the other hand, Albutein[®] and Flebogamma[®] DIF are safe products that are widely used worldwide. For special warnings and precautions see the corresponding **Full Prescribing Information (Appendix 1 and 2)**.

5.2.2.1 Hypocalcemia

The great majority of side effects associated with plasma exchange apheresis is due to the administration of citrate and are related to diminish ionic calcium availability. Although some

adverse reactions not explainable in terms of hypocalcemia, or not resolved by calcium dosing, may be attributable to citrate interaction with magnesium (of characteristics similar to those of calcium).

When volume replacement is performed with 5% albumin, the risk of hypocalcemia is considerably lower than when plasma is used for replacement (seen historically in approximately 7.8% of sessions), and no important toxicity is detected.

The factors predisposing to hypocalcemia may be patient-related (hypoalbuminemia, vitamin D deficiency (malnutrition, malabsorption), hypomagnesemia, hyperphosphatemia, altered liver or kidney function or hypoparathyroidism) or related to the procedure (duration of citrate infusion >120 minutes, respiratory alkalosis generally induced by tachypnea).

All plasma exchanges produce transient hypocalcemia that is usually well tolerated by the patient. Occasionally, the decrease in ionic calcium levels can increase nerve cell membrane excitability, resulting in symptoms.

The symptoms and signs of hypocalcemia to be assessed are:

- paresthesias
- headache
- vision alterations (glinting)
- nausea
- cramps
- chest oppression

The degree of hypocalcemia is rated from 0 to 4 as follows:

| Level | Symptoms | Treatment |
|-------|------------------------------------|---|
| 0 | None | None |
| 1 | Reported by patient, and tolerable | Calcium p.o. (Sandosten Calcium) |
| 2 | Cause discomfort | Infusion of CaCl ₂ i.v. |
| 3 | Important discomfort | Reduce flow 20% Infusion of CaCl ₂ i.v. |
| 4 | Unbearable | Stop procedure Infusion of CaCl ₂ i.v. |

Treatment is with a calcium chloride infusion, which may cause arrhythmias. The calcium chloride formulation must be infused diluted in physiological saline solution, at a maximum concentration of 2 mg/mL.

As each infused milliliter of acid citrate-dextrose A (ACD-A) neutralizes 0.5 mg of calcium, the calcium chloride dose will be equal to the milliliters of ACD-A infused in the last hour multiplied by 0.5 and by the calcium chloride concentration of the dilution employed (2 mg/mL), using the following formula:

$$\text{Volume of calcium chloride} = \text{Volume of ACD-A (last hour)} / 4$$

The formulation is administered via drip through the return catheter, in 10-15 minutes. This rate may vary according to whether the symptoms improve or not.

If the patient shows **Level 2** symptoms from the start or before the first 120 minutes of replacement, prophylactic blood calcium treatment should be provided. A 0.2 mg/mL calcium chloride solution is prepared and infused through the return catheter. To calculate the infusion rate, the following must be applied:

- Correcting factor of the amount of ACD-A/ml citrated blood
- Proportion of ACD-A / blood
- Access flow

Table 1 below specifies the calcium chloride infusion rate (concentration 2 mg/mL) when administered prophylactically on a continuous basis according to the separator inlet flow, the proportion ACD-A / blood, and the correction factor.

Administration of CaCl₂

CaCl₂ infusion rate in ml/hour (concentration 2 mg/ml) according to inflow rate and ACD-A: blood ratio

| Ratio | Flow (ml/min) | | | | | | | | | | | | | | | | | | | | | | | |
|-------|---------------|----|----|----|----|----|----|----|----|----|----|----|----|-----|-----|-----|-----|-----|-----|-----|-----|-----|-----|-----|
| | 15 | 20 | 25 | 30 | 35 | 40 | 45 | 50 | 55 | 60 | 65 | 70 | 75 | 80 | 85 | 90 | 95 | 100 | 105 | 110 | 115 | 120 | 125 | 130 |
| 1:30 | 7 | 9 | 12 | 14 | 16 | 19 | 21 | 23 | 26 | 28 | 30 | 32 | 35 | 37 | 39 | 42 | 44 | 46 | 49 | 51 | 53 | 56 | 58 | 60 |
| 1:29 | 7 | 10 | 12 | 14 | 17 | 19 | 22 | 24 | 26 | 29 | 31 | 34 | 36 | 38 | 41 | 43 | 46 | 48 | 50 | 53 | 55 | 58 | 60 | 62 |
| 1:28 | 7 | 10 | 12 | 15 | 17 | 20 | 22 | 25 | 27 | 30 | 32 | 35 | 37 | 40 | 42 | 45 | 47 | 50 | 52 | 55 | 57 | 60 | 62 | 65 |
| 1:27 | 8 | 10 | 13 | 15 | 18 | 21 | 23 | 26 | 28 | 31 | 33 | 36 | 39 | 41 | 44 | 46 | 49 | 52 | 54 | 57 | 59 | 62 | 64 | 67 |
| 1:26 | 8 | 11 | 13 | 16 | 19 | 21 | 24 | 27 | 29 | 32 | 35 | 37 | 40 | 43 | 45 | 48 | 51 | 54 | 56 | 59 | 62 | 64 | 67 | 70 |
| 1:25 | 8 | 11 | 14 | 17 | 19 | 22 | 25 | 28 | 31 | 33 | 36 | 39 | 42 | 45 | 47 | 50 | 53 | 56 | 58 | 61 | 64 | 67 | 70 | 72 |
| 1:24 | 9 | 12 | 14 | 17 | 20 | 23 | 26 | 29 | 32 | 35 | 38 | 41 | 43 | 46 | 49 | 52 | 55 | 58 | 61 | 64 | 67 | 70 | 72 | 75 |
| 1:23 | 9 | 12 | 15 | 18 | 21 | 24 | 27 | 30 | 33 | 36 | 39 | 42 | 45 | 48 | 51 | 54 | 57 | 60 | 64 | 67 | 70 | 73 | 76 | 79 |
| 1:22 | 9 | 13 | 16 | 19 | 22 | 25 | 28 | 32 | 35 | 38 | 41 | 44 | 47 | 51 | 54 | 57 | 60 | 63 | 66 | 70 | 73 | 76 | 79 | 82 |
| 1:21 | 10 | 13 | 17 | 20 | 23 | 26 | 30 | 33 | 36 | 40 | 43 | 46 | 50 | 53 | 56 | 60 | 63 | 66 | 70 | 73 | 76 | 79 | 83 | 86 |
| 1:20 | 10 | 14 | 17 | 21 | 24 | 28 | 31 | 35 | 38 | 42 | 45 | 49 | 52 | 56 | 59 | 63 | 66 | 70 | 73 | 77 | 80 | 83 | 87 | 90 |
| 1:19 | 11 | 15 | 18 | 22 | 26 | 29 | 33 | 37 | 40 | 44 | 48 | 51 | 55 | 59 | 62 | 66 | 70 | 73 | 77 | 81 | 84 | 88 | 92 | 95 |
| 1:18 | 12 | 15 | 19 | 23 | 27 | 31 | 35 | 39 | 43 | 46 | 50 | 54 | 58 | 62 | 66 | 70 | 73 | 77 | 81 | 85 | 89 | 93 | 97 | 100 |
| 1:17 | 12 | 16 | 20 | 25 | 29 | 33 | 37 | 41 | 45 | 49 | 53 | 57 | 61 | 65 | 70 | 74 | 78 | 82 | 86 | 90 | 94 | 98 | 102 | 106 |
| 1:16 | 13 | 17 | 22 | 26 | 30 | 35 | 39 | 43 | 48 | 52 | 57 | 61 | 65 | 70 | 74 | 78 | 83 | 87 | 91 | 96 | 100 | 104 | 109 | 113 |
| 1:15 | 14 | 19 | 23 | 28 | 32 | 37 | 42 | 46 | 51 | 56 | 60 | 65 | 70 | 74 | 79 | 83 | 88 | 93 | 97 | 102 | 107 | 111 | 116 | 121 |
| 1:14 | 15 | 20 | 25 | 30 | 35 | 40 | 45 | 50 | 55 | 60 | 65 | 70 | 75 | 79 | 84 | 89 | 94 | 99 | 104 | 109 | 114 | 119 | 124 | 129 |
| 1:13 | 16 | 21 | 27 | 32 | 37 | 43 | 48 | 54 | 59 | 64 | 70 | 75 | 80 | 86 | 91 | 96 | 102 | 107 | 112 | 118 | 123 | 128 | 134 | 139 |
| 1:12 | 17 | 23 | 29 | 35 | 41 | 46 | 52 | 58 | 64 | 70 | 75 | 81 | 87 | 93 | 99 | 104 | 110 | 116 | 122 | 128 | 133 | 139 | 145 | 151 |
| 1:11 | 19 | 25 | 32 | 38 | 44 | 51 | 57 | 63 | 70 | 76 | 82 | 89 | 95 | 101 | 107 | 114 | 120 | 126 | 133 | 139 | 145 | 152 | 158 | 164 |

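### Protocol 5.2.2.1 has sites prepare prophylactic calcium chloride at 0.2 mg/mL, but the only usable infusion rates (Table 1) are for 2 mg/mL, a tenfold mismatch

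*Protocol*

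**What the plan says.** Protocol 5.2.2.1 (Hypocalcemia) describes two uses of intravenous calcium chloride.

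- **Treatment dose.** The solution may not exceed 2 mg/mL. The dose starts from a stated equivalence: "As each infused milliliter of acid citrate-dextrose A (ACD-A) neutralizes 0.5 mg of calcium". The volume is then described as the last hour's ACD-A "multiplied by 0.5 and by the calcium chloride concentration of the dilution employed (2 mg/mL), using the following formula", and the printed formula is that ACD-A volume divided by 4. It is given over 10 to 15 minutes.
- **Prophylactic continuous infusion.** The trigger is Level 2 "symptoms from the start or before the first 120 minutes of replacement, prophylactic blood calcium treatment should be provided". The preparation instruction is "A 0.2 mg/mL calcium chloride solution is prepared and infused through the return catheter". Three items are listed for calculating the rate: the ACD-A-to-blood proportion, the access flow, and a "Correcting factor of the amount of ACD-A/ml citrated blood". No value for that factor and no formula are given. The rates come from a table introduced as "Table 1 below specifies the calcium chloride infusion rate (concentration 2 mg/mL) when administered prophylactically on a continuous basis" and headed with an "infusion rate in ml/hour (concentration 2 mg/ml) according to inflow rate and ACD-A: blood ratio".

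**The concern.** One sentence sets the strength at 0.2 mg/mL, and the next paragraph supplies rates for the same infusion at 2 mg/mL. Because the correction factor has no stated value, a site cannot work out its own rate for a 0.2 mg/mL solution and has to use Table 1. If the bag is made up as instructed and run at the tabulated mL/h, the patient receives a tenth of the dose the table is built to give. The section's only explicit limit on strength is an upper one, so it would not flag an error on the low side.

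There is also a smaller wording defect. The sentence leading into the treatment formula says to multiply by the concentration, whereas the formula divides by it.

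**Working it through.** **Inputs, all from Protocol 5.2.2.1:** 0.5 mg neutralized per mL of ACD-A; Table 1 with 20 ratios (1:30 to 1:11) by 24 flows (15 to 130 mL/min), i.e. 480 cells in whole mL/h; strengths of 2 and 0.2 mg/mL. Milligrams are used as the protocol uses them.

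**1. Reproduce the table.** For ratio 1:r and flow f in mL/min:

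- ACD-A per hour = 60 × f / r
- rate (mL/h) = k × 0.5 × ACD-A per hour / strength, rounded to a whole number

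The constant k stands in for the unstated correction factor. At 2 mg/mL, any k from 0.92734 to 0.92745 reproduces 480 of 480 cells. With k = 0.9274 and 0.2 mg/mL, 0 of 480 cells are reproduced. To fit the table at 0.2 mg/mL, k would have to be about 0.0927, meaning that the infusion replaces about 9% of the calcium the section says is neutralized.

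**2. One cell in full (1:14, 60 mL/min; printed rate 60 mL/h).**

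- ACD-A per hour = 60 × 60 / 14 = 257.1 mL
- Calcium neutralized = 0.5 × 257.1 = 128.6 mg/h
- With k: 0.9274 × 128.6 = 119.2 mg/h
- At 2 mg/mL: 119.2 / 2 = 59.6, which rounds to the printed 60 mL/h
- At 0.2 mg/mL: 119.2 / 0.2 = 596 mL/h, against the printed 60

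Without any factor, 257.1 / 4 = 64.3 mL/h, so the table sits about 7% below the ACD-A/4 rule. That gap is the fitted k and has no bearing on the tenfold difference.

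**3. Dose if 0.2 mg/mL is run at the table rate.**

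| Setting | Table rate (mL/h) | mg/h at 2 mg/mL | mg/h at 0.2 mg/mL |
|---|---|---|---|
| 1:14, 60 mL/min | 60 | 120 | 12 |
| 1:14, 100 mL/min | 99 | 198 | 19.8 |
| 1:20, 80 mL/min | 56 | 112 | 11.2 |
| Whole table | 7 to 164 | 14 to 328 | 1.4 to 32.8 |

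The ratio is 0.2 / 2 = 0.10 in every cell, whatever the value of k. Suppose the 60 to 100 mL/min session rate in Protocol 5.1.3 is the inlet flow (an assumption). The tabulated rates are then 28 to 126 mL/h, and matching the table's dose with a 0.2 mg/mL solution would need 280 to 1,260 mL/h.

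**4. The treatment-dose wording, per mL of ACD-A.** The formula gives 0.5 / 2 = 0.25 mL, i.e. 0.5 mg. Taken literally, the words give 0.5 × 2 = 1. Read as mg, that is 1 / 0.5 = 2 times the formula's dose. Read as mL, it is 2 mg, or 2 / 0.5 = 4 times.

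**The case against.** The intended strength can be recovered from the text alone. Section 5.2.2.1 gives 2 mg/mL four times (the maximum, the dilution for the treatment dose, the Table 1 lead-in and the table heading) and 0.2 mg/mL once. Under-dosing requires a site to follow that one sentence and overlook two labels next to the rates. This stands and limits the severity, but the operative preparation sentence remains wrong.

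A reader might infer that symptomatic patients would be left with a tenth of the calcium they need. The documents do not support that. Level 2 in the severity table already calls for intravenous calcium chloride, dosed by the ACD-A/4 rule at 2 mg/mL, and Levels 3 and 4 reduce the flow or stop the procedure. Only the additional continuous infusion would be weak. Specialists supervise continuously and the physician decides on any incident (5.2.2, 5.6), and calcium is measured before and after each full exchange (6.2.2, Appendix 8). Section 5.2.2.6 also defers to local procedures, although whether that reaches back to hypocalcemia is arguable.

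A reader might also use the historical 7.8% of sessions in 5.2.2.1 to count affected exchanges. That figure cannot cover all hypocalcemia, because the same section says every exchange lowers calcium transiently. Nor does it isolate Level 2 symptoms before 120 minutes.

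Finally, 5.2.2 extends its guidance to the low-volume period, which might suggest that the error applies there too. Table 1 is indexed to ACD-A, whereas the Auto-C materials (Appendix 3a) list sodium citrate, and Aurora (Appendix 3b) uses sodium citrate or ACD-A depending on configuration. Section 5.2.2 also expects far fewer adverse events in that period. The point is therefore not extended to it.

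The multiplication wording is minor, since the printed formula is the working instruction.

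**Conclusion.** The point holds as an internal contradiction in an intravenous preparation instruction: 0.2 mg/mL is wrong as written, and the evidence within the section points to 2 mg/mL. If the solution is prepared as stated and run at the table rate, the prophylactic infusion delivers one tenth of the table's dose. That factor needs no assumption beyond using the two figures together. The fitted 0.927 serves only to show which strength the table was built for; it is inferred from the table and not stated in the protocol.

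The risk is conditional and mitigated, and the number of sessions in which it could arise is unknown. It should be fixed, but the documents do not show that harm would follow. The check shows internal consistency only. It does not validate the dose clinically, and the section mixes mg of calcium (the 0.5 mg equivalence) with mg/mL of calcium chloride. Power, type I error and the efficacy analyses are unaffected.

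**What to change.** - In Protocol 5.2.2.1, change the strength of the prophylactic solution from 0.2 mg/mL to 2 mg/mL, after the sponsor's apheresis experts have confirmed it, and notify sites.
- In the same edit, reword the treatment-dose sentence so that the ACD-A volume is multiplied by 0.5 and divided by the concentration, matching the printed ACD-A/4 formula (minor).
- While confirming, the experts could usefully state the value of the correction factor behind Table 1 and whether mg refers to calcium or to calcium chloride.

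The cost is two text edits, one clinical confirmation and one site notice. The design, sample size and analysis do not change.
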